## **8. Benefits**

### **Potential Benefits to Participants**

During the open pilot (e.g., aim 2), we expect that participants may experience benefits including improvement in physical (self-report, performance, and objective) and emotional (depression and anxiety) function, increases in coping ability, and decrease in catastrophizing and fear of pain. These participants are also expected to benefit from the support of the therapist and group members. The knowledge gained from the research will benefit others by answering questions regarding effective nonpharmacological strategies to provide treatment for chronic pain in this population. Interested participants may also be sent a copy of publications from the open pilot once available. The risks to subjects are reasonable in relation to the anticipated benefits to research participants and others. The risks for participation in both the intervention and assessments are minimal, while the potential benefits are substantial.

### **Potential Benefits to Society**

Our goal is to learn more about the feasibility, acceptability, and fidelity of implementing a group medical visit program in the primary care setting for older adults with chronic pain in underserved communities. We believe that the open pilot will provide insight into what individual, provider, community and environmental/systemic changes are possible and which of these changes may best support treatment for chronic pain in older, ethnically diverse adults. Chronic pain is prevalent and costly, particularly among underserved minority groups. Current standards for psychosocial interventions have several limitations including underwhelming

improvements in pain outcomes, in particular performance based and ambulatory activity (step count). As previously mentioned, the open pilot will enable us to establish the feasibility, acceptability, and fidelity of *GetActive+* program and study procedures. We will use this knowledge to further optimize the program in preparation for the R33 phase of this project as well as future studies and may ultimately help researchers and clinicians better care for patients with chronic pain.

## 9. Statistical Analysis

Aim 2 open pilot data analysis will be conducted with the primary goal of establishing feasibility as opposed to powering for specific effects for the quantitative outcomes. We propose *a priori* benchmarks for feasibility, acceptability and fidelity based upon our prior research and recommendations in the field (see Table 4). Since this pilot study was powered for establishing feasibility, we will assess preliminary efficacy by testing for signals of improvement in our secondary outcomes. We will first examine the distribution and normality of the data through a combination of histograms and the Shapiro-Willks test, and then conduct pre-post comparisons using paired t-tests or the Wilcoxon signed rank test as the non-parametric equivalent. Cohen's d effect sizes will be interpreted using the following pilot-recommended guidelines: small (Cohen's d = 0.2), medium (Cohen's d = 0.5), and large (Cohen's d = 0.8). For outcomes analyzed with the Wilcoxon signed rank test, we will calculate effect size via the equation  $r=Z/\sqrt{N}$ .

Table 4. Measurement of mixed methods implementation outcomes across both phases based upon Aarons' model and Proctor's framework for defining implementation outcomes.

Implementation Outcome	Definition	Recommended Implementation Step in Aarons' Model	Study Aim	Assessment modality (multi-level, mixed methods assessments); Go/No-Go Benchmarks
Feasibility	Suitability and practicality	Early (steps 1-3)	R61 Aim 2; R33 Aim 3	>= 75% agree to participate in intervention; qualitative feedback (patients; R61 Aim 2; patients and staff and clinicians R33 Aim 3).
Acceptability	Satisfaction with or tolerability of the proposed approach	Early (Steps 1-3)	R61 Aim 2; R33 Aim 3	>=75 enrolled complete >=75 sessions; qualitative feedback (patients; R61 Aim 2 and patients, and staff and clinicians R33 Aim 3).
Fidelity	Delivery of GetActive+ as intended	Early to Mid (Steps 2-3)	R61 Aim 2; R33 Aim 3	>=75% of sessions components delivered by clinicians in the clinic as intended; 20% sessions rated
Adoption	Uptake, intent to implement by organization, clinicians	Early to Mid (Steps 1-4)	R33 Aim 3	Qualitative assessment by staff and clinicians; intention to adopt.

Effect sizes will be interpreted using values commonly published in the literature for non-parametric measures: small ( $r=0.10 - <0.3$ ), moderate ( $r=0.30 - <0.5$ ) and large ( $r \geq 0.5$ ). SPSS Version 28 will be used for all quantitative analyses.

We will utilize rapid data analysis (RDA) to analyze the exit interview data. We will review each transcript in the 24 hours after the interview and then create an RDA matrix to better synthesize responses and inform manual revisions. The matrix format will be synthesized using a deductive approach based on the domains outlined in the guide: Domain 1: The *GetActive+* Program, Domain 2: *GetActive+* Skills, Domain 3: Clinician and Nurse Practitioner, Domain 4: Assessments, Domain 5: Group Session Modality, Domain 6: Home Practice, Domain 7: Individualized Barriers and Facilitators. Our team has used these methods in prior work in community clinics which gives confidence that these procedures are feasible and effective in detecting nuanced aspects of program and protocol adaptation to inform subsequent implementation of the proposed changes.

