## 2. Specific Aims and Objectives

Conduct an open pilot trial (i.e., Aim 2 of P# 2022P001691) of the *GetActive+* program (i.e., a novel mind-body and activity program) followed by optional qualitative exit interviews with RHC patients (up to N=50). We will determine if the feasibility, acceptability, and fidelity of the program meet *a priori* benchmarks. We also hope to establish preliminary efficacy that the program improves physical function and other study outcomes we describe in sections below. We will use qualitative data to optimize the intervention and study procedures for future trials. See Figure 2 for aim 2 study schema.

Figure 2. Aim 2 Study Schema

\*Total number of patient participants (up to N=50)

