or remotely (i.e., over Zoom). In the event that exit interviews are conducted virtually, we will use an MGB Zoom account. Zoom specifically states that their software is equipped to keep information secure, and the software does not have access to identifiable information. Zoom is HIPPA compliant, MGB approved, and the current video software standard for patient care within our Department of Psychiatry. We will audio record the focus groups with consent from participants using MGB encrypted devices. We will transcribe recordings after each group and use these transcriptions to conduct qualitative analyses. No PHI will be included in the transcriptions. Outcomes will be used to guide subsequent manual adaptations and protocol, training, and fidelity procedures for the *GetActive+* program.

At the end of study enrollment (e.g., no longer recruiting/enrolling participants or conducting follow-ups with participants), we will conduct open-ended focus group or individual interviews with up to 20 participants who have completed the study. These group or individual interviews will be used to inform the future development of the program and to understand ways to better teach session content to increase understanding and engagement. Participants will be selected based on clinician perception on improvement and benefit and ability to engage in the material in a meaningful way. Interested participants will verbally consent after receiving a study fact sheet. Since we will be pulling from individuals who previously enrolled, we will only be re-consenting individual who choose to participate. We will contact participants via phone to gauge interest in participating, and the focus groups or individual interviews will be conducted in-person for up 60 minutes. We will be compensating participants an additional \$40 for their participation.

Our primary outcomes for the open pilot will be the feasibility, acceptability, and fidelity of the *GetActive+* program. Preliminary effectiveness outcomes will also be examined (e.g., multimodal physical function (self-report, 6-minute walk test and activity level measured via ActiGraph) and emotional function (depression and anxiety)).

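### A normality check decides whether each pre-post effect is labelled on Cohen's d or on r, two scales that do not match, and the paired tests leave out anyone without both values

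*Combined protocol and SAP*

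**What the plan says.** The combined protocol and SAP (section 9, Statistical Analysis) first looks at the data through "a combination of histograms and the Shapiro-Willks test". It then compares pre and post by "paired t-tests or the Wilcoxon signed rank test as the non-parametric equivalent".

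- **First effect scale.** Cohen's d: "effect sizes will be interpreted using the following pilot-recommended guidelines", namely 0.2 small, 0.5 medium and 0.8 large.
- **Second effect scale.** "For outcomes analyzed with the Wilcoxon signed rank test, we will calculate effect size via the equation" r = Z/√N. Its ranges are introduced by "Effect sizes will be interpreted using values commonly published in the literature for non-parametric measures": 0.10 to under 0.3 small, 0.30 to under 0.5 moderate, 0.5 and above large.

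The section does not give a threshold for the normality test, whether scores or changes are checked, the SD that goes into d, what N counts in r, an analysis set for these outcomes, or a way to handle missing values.

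Section 2 sets the ambition: "We also hope to establish preliminary efficacy that the program improves physical function and other study outcomes". Section 6 adds: "Preliminary effectiveness outcomes will also be examined", naming self-reported function, 6-minute walk, activity level, depression and anxiety. Section 6 also expects about 20% attrition. Table 2 schedules nearly all of the outcome measures at pre and post only.

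**The concern.** With no powered test of these outcomes, the effect-size labels are a main product of the efficacy analysis. If step count goes to Wilcoxon and depression to the t-test, a reader who sees *large* for one and *medium* for the other cannot tell whether the improvements differ or only the scales do. A data-dependent check decides which scale applies.

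The second part is independent of the first. A paired t-test or signed-rank test uses only people with both values. If those who miss the post assessment differ at baseline from those who attend, the change among complete pairs is not the change among all enrolled, and the error can go either way.

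**Working it through.** The plan states no effect, power or alpha for these outcomes, so there is no figure of its own to reproduce. The check puts d and r on one scale and then looks at complete pairs.

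**1. From d to r.** Assume normally distributed changes, with d on the SD of change. In large samples, with N = pairs,

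r = √3 × (Φ(√2 × d) − 0.5).

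If N counts observations (two per person), divide by √2.

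| d | r, N = pairs | r, N = observations |
|---|---|---|
| 0.20 | 0.193 | 0.136 |
| 0.50 | 0.451 | 0.319 |
| 0.60 | 0.523 | 0.370 |
| 0.80 | 0.643 | 0.454 |

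**2. The r cut-offs expressed as d.** Inverting, d = Φ⁻¹(0.5 + r/√3)/√2, with r multiplied by √2 first if N counts observations.

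| r cut-off | d, N = pairs | d, N = observations |
|---|---|---|
| 0.10 | 0.103 | 0.146 |
| 0.30 | 0.317 | 0.466 |
| 0.50 | 0.567 | 0.940 |

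Neither column is 0.2/0.5/0.8.

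- *N = pairs.* d = 0.60 is *medium* whether the three d points are read as lower bounds or as nearest values (midpoints 0.35 and 0.65), but r = 0.52 is *large*.
- *N = observations.* d = 0.60 gives r = 0.37, *moderate*, so the labels agree. From d = 0.80 to 0.94, d is *large* and r only *moderate*.

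The nearest hint about N is in section 2, "Total number of patient participants (up to N=50", which is a cap on enrolment and does not define N in a paired-test formula.

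**3. If d uses the baseline SD.** With equal SDs pre and post, the SD of change is √(2(1 − ρ)) baseline SDs, where ρ is the pre-post correlation (assumed). For d = 0.60 and N = pairs:

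- ρ = 0.3: 0.60/1.183 = 0.507, so r = 0.46, *moderate*.
- ρ = 0.7: 0.60/0.775 = 0.775, so r = 0.63, *large*.

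**4. Size against sampling error.** The standard error of d is about 0.30 at 12 pairs (3 groups × 5 × 0.8) and 0.17 at 40 pairs (50 × 0.8). With N = pairs, the zones where r is labelled higher under both readings of the d points are 0.32–0.35 and 0.57–0.65, narrower than that error.

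**5. How often it would happen.** This cannot be fixed from the documents. Simulations of outcomes both sent to Wilcoxon and labelled higher on r, with N = pairs and an assumed 0.05 gate, ran from 0% to 50% according to the assumed distribution, number of pairs and reading of the d points. For normal changes the figure was 1–3%.

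**6. Complete pairs.** Assumptions: baseline X standard normal; true mean change 0.40 baseline SD; equal SDs; correlation ρ; 20% missing post values with a logit slope s on X. Then

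complete-pair mean change = 0.40 − (1 − ρ) × E[X | post value present].

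The conditional mean is ∓0.096 for s = ±0.5 and ∓0.173 for s = ±1.

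| s | ρ = 0.3 | ρ = 0.5 | ρ = 0.7 |
|---|---|---|---|
| −1 | 0.279 | 0.313 | 0.348 |
| −0.5 | 0.333 | 0.352 | 0.371 |
| +0.5 | 0.467 | 0.448 | 0.429 |
| +1 | 0.521 | 0.487 | 0.452 |

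A likelihood model that also uses the baselines of people with no post value recovers 0.40 (0.398–0.401 in simulation). At s = ±1 and ρ = 0.5 the bias of about 0.09 compares with a simulated SD of the estimate of about 0.29 with 15 enrolled and 0.16 with 50: roughly 0.3 and 0.55 standard errors.

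**The case against.** The strongest case against runs as follows.

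- **The labels agree at the plan's own d points.** With N = pairs, 0.2, 0.5 and 0.8 give r of 0.19, 0.45 and 0.64, which carry the matching labels. This stands. The mismatch lies between the points and is small against sampling error. It is systematic, though, and would not shrink with more data.
- **Direction is undetermined.** A reader might infer that r flatters the result. The documents do not support that: it needs N = pairs and suitable SD conventions, and the plan states neither. Only non-equivalence is established.
- **The check is not a mechanical gate.** Histograms are used together with the test, so simulated frequencies at a 0.05 threshold are illustrations. This stands, and no frequency should be carried forward.
- **No decision uses the labels.** Feasibility is the primary goal, and no text says labels will be ranked across outcomes. This stands, and it limits the severity.
- **Complete-pair analysis is not written in the plan.** It follows from the paired tests and the absence of any other rule. A reader might also infer that 20% of post values will be missing. Section 6 gives that figure as a retention estimate, and someone who stops sessions but attends the post assessment still contributes a pair.
- **The model is not a cure.** If people who improve less leave more often, simulations under similar assumptions gave 0.47–0.60 from complete pairs and 0.46–0.54 from the likelihood model, for a true 0.40. This stands and must be said beside the result.

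**Conclusion.** The concern holds in limited form. Section 9 labels pre-post effects on two scales that are not equivalent, chosen outcome by outcome after a look at the data. For normal changes with d on the SD of change, the r cut-offs equal d of 0.10/0.32/0.57 (N = pairs) or 0.15/0.47/0.94 (N = observations). Labels cannot be compared across outcomes on different branches. Whether r comes out higher or lower cannot be said until N and the SD are defined.

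The missing-value part also holds. Under the assumed baseline-related drop-out, complete pairs would give 0.28–0.52 for a true 0.40, a modest bias against the sampling error of a pilot. The true share of missing post values may differ from 20%.

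Severity is minor. A reader might infer that the decision to proceed is at risk, but the Table 4 go/no-go benchmarks rest on participation, session completion and delivery, with qualitative feedback, and use none of these effect sizes. Only secondary preliminary signals are affected.

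**What to change.** This is a cheap improvement to section 9.

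1. For every outcome measured both pre and post (so not the post-only global impression of change or the weekly pacing questionnaire), report the mean change with a 95% CI and one standardised effect, with a named SD and one set of label ranges, whatever the normality check shows.
2. Wilcoxon may be reported beside it. If r is kept, define N and do not label it on a second scale.
3. Estimate the change with a likelihood-based repeated-measures model (SPSS MIXED) using all enrolled participants with any assessment. State that it is unbiased only if drop-out depends on observed values, and show the complete-pair result beside it.
4. Optionally, add an analysis that sets drop-outs to no change, noting that it understates the effect when drop-out is unrelated to outcome (0.8 × 0.40 = 0.32).

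Cost: SAP wording and a little more analysis in software already planned, with no new data. Downsides: some labels may become less favourable, and mean-based effects are less robust for skewed outcomes, which is a reason to keep the Wilcoxon result visible.

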### 3. General Description of Study Design

We will conduct an open pilot trial of the *GetActive+* program followed by individual qualitative exit interviews. We plan to conduct 3-6 groups of approximately 5-10 participants each (up to N=50). At least one of the 3-6 groups will be offered in Spanish and led by a fully trained Spanish speaking social worker and member of study staff. The goal of this phase will be to establish feasibility (primary), acceptability, and fidelity of the *GetActive+* program and study procedures. We will also explore improvements in study outcomes. We will recruit English and Spanish speaking older adults (55+) with chronic pain currently receiving medical care from RHC. Recruitment will be facilitated through posted IRB approved flyers, in-clinic approaches made by study staff, and referrals from RHC physicians, nurses, psychologists and other relevant staff (see section 4). These recruitment strategies are informed by recommendations from RHC staff and are supported by [REDACTED]. If patients indicate interest in participating, they will be guided through eligibility screening by study staff (see section 4). After screening, interested patients will discuss their availability for a baseline visit and the 10-week *GetActive+* program. A Research Assistant (RA) will keep track of potential participant preferences with regard to the days and times for intervention delivery and in person versus remote participation. The number of participants per group will vary based on availability, while typically ranging between 3 and 10. At the subsequent in person baseline assessment, patients will provide their informed consent in the presence of study staff and complete all assessments. They will also pick up their ActiGraph watch to wear for 7-10 days (see section 6). They will later return their ActiGraph either in person or in the mail via pre-paid envelop. These same procedures will be followed for Spanish speaking patients. All Spanish speaking patient interactions will be conducted by a native Spanish speaking RA. Additionally, all study materials have either already been translated and validated or will be translated into Spanish by a translation service or a native Spanish-speaking researcher.

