Adaptive coping	Self-Compassion Scale – Short Form (SCS-SF) ; assesses participants’ capacity for self-compassion. Pre, post  Gratitude Questionnaire (GQ-6) assesses individual differences in the proneness to experience gratitude in daily life. Pre, post  Applied Mindfulness Process Scale (AMPS) ; assesses how participants’ use mindfulness when facing challenges in daily life. Pre, post  Cognitive and Affective Mindfulness Scale – Revised (CAMS-R) ; measures mindfulness and the degree to which respondents’ experience thoughts and feelings. Pre, post  Measure of Current Status (MOCS) ; assesses current self-perceived status on the ability to relax at will, recognize stress-inducing situations, restructure maladaptive thoughts, be assertive about needs, and choose appropriate coping responses as needed. Pre, post

The *GetActive+* program will be conducted either virtually or in person (depending on patients’ preferences) by trained staff (psychologist or nurse practitioner, or both depending on availability) over the course of 10 weekly sessions. It is important that all eligible patients be able to participate should they choose to enroll. Thus, participants that wish to attend virtually but do not have the appropriate technology will be provided with a smart device, the type of which will be dependent on study funds and device availability. Prior to or directly after each session, participants will have the option to attend a 5-10 minute 1-on-1 medical check-in with the nurse practitioner. The purpose of these check-ins is to ensure that participants feel

physically safe and comfortable with the activity-based component of the program throughout the duration of their participation. Each of the 10 sessions will last approximately 60-minutes. Group sizes will be approximately 3-10 participants, however, this may be subject to change depending on the rate of attrition. Currently, we estimate approximately 20% attrition with the understanding that participant retention for this population might be less than what was observed in prior trials with *GetActive*. The interventionist will be trained by [name] and [name] and supervised weekly.

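### Section 9 labels effect sizes from the point estimate, with no confidence interval and no link to the paired test; with about 12 to 40 completers the label conveys little about precision

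*Combined protocol and SAP*

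**What the plan says.** Section 9 looks for signals of improvement in the secondary outcomes. After checking distributions, the team will "conduct pre-post comparisons using paired t-tests or the Wilcoxon signed rank test as the non-parametric equivalent". Two labelling rules follow. For the parametric route, Cohen's d "effect sizes will be interpreted using the following pilot-recommended guidelines: small" and upward; the anchors in full are "small (Cohen's d = 0.2), medium (Cohen's d = 0.5), and large (Cohen's d = 0.8"). For the Wilcoxon route, r = Z/√N is computed and "Effect sizes will be interpreted using values commonly published in the literature for non-parametric measures": small from 0.10, moderate from 0.30, large from 0.50.

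Section 9 names no confidence interval for any effect size and states no alpha. It does not define the SD that standardises d, and it does not make a label depend on the test. It does say that the pilot is aimed at feasibility and is not powered for specific effects.

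On numbers, Section 3 says "We plan to conduct 3-6 groups of approximately 5-10 participants each (up to N=50"), and later in the same section: "The number of participants per group will vary based on availability, while typically ranging between 3 and 10". Section 6, in the text after Table 2, says: "Currently, we estimate approximately 20% attrition".

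**The concern.** A verbal label on a standardised point estimate says how large the estimate is and nothing about how well it is known. With a dozen to forty paired observations the sampling error of d is comparable to the distance between adjacent anchors. A label can therefore be crossed by chance, and two results with the same label can carry very different amounts of evidence.

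What is at stake is how preliminary efficacy is read. Section 2 hopes to establish it, Section 6 names preliminary effectiveness outcomes, and Section 8 says that what is learned will prepare the R33 phase. A table of small, medium and large labels without intervals could be taken forward as firmer support than the data give. The planned tests supply p-values. Those do not show the range of effects compatible with the data, and the text does not reserve the labels for results that pass a test.

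**Working it through.** The plan states no power, SD or precision figure for the effect sizes, so there is no figure of its own to reproduce. The check below uses its planned numbers.

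**Completers.** Lowest planned total: 3 groups × 5 = 15, and 15 × 0.8 = 12. Cap: 50 × 0.8 = 40. For an intermediate case, 6 groups × 5 (or 3 × 10) = 30, and 30 × 0.8 = 24. Section 3 also allows groups of 3; three of those give 9 × 0.8 ≈ 7, so 12 is not the worst case.

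**Assumptions, because the documents are silent.** Two-sided 95% level; d = mean change / SD of change; the anchors for d read as thresholds (d ≥ 0.2, d ≥ 0.5). Bands are written out only for r.

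**Formulas.**
- Interval for d: with t = d√n on n−1 degrees of freedom, find the two noncentrality values that place the observed t at the 97.5th and 2.5th percentiles of the noncentral t, then divide each by √n.
- Chance label in the improvement direction with no true change: P(t with n−1 df ≥ c√n) for d; P(Z ≥ c√n) for r (normal approximation).
- Example at n=12: 0.2 × √12 = 0.693, and P(t with 11 df ≥ 0.693) = 0.251.

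| | n=12 | n=24 | n=40 |
|---|---|---|---|
| 95% CI, observed d = 0.5 | -0.11 to 1.09 | 0.07 to 0.92 | 0.17 to 0.83 |
| 95% CI, observed d = 0.2 | -0.38 to 0.77 | -0.21 to 0.60 | -0.11 to 0.51 |
| No true change: P(d ≥ 0.2) | 25% | 17% | 11% |
| No true change: P(d ≥ 0.5) | 5.6% | 1.1% | 0.15% |
| No true change: P(r ≥ 0.10) | 36% | 31% | 26% |
| Two-sided p at d = 0.2 | 0.50 | 0.34 | 0.21 |
| Two-sided p at d = 0.5 | 0.11 | 0.022 | 0.003 |

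A simulated Wilcoxon null agrees with the normal approximation: P(|r| ≥ 0.10) is 0.732 against 0.729 at n=12, and 0.527 by both at n=40. Half of each is the one-direction figure.

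**Where the 'medium' interval reaches zero.** For d = 0.5 the lower limit is -0.01 at n=17 and 0.00 (just above zero) at n=18. At 20% attrition, 17 completers correspond to 17 / 0.8 ≈ 21 enrolled.

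**Expected chance labels if no outcome truly changes.** Section 6 gives five effectiveness outcomes as examples: self-reported function, 6-minute walk, ActiGraph activity, depression and anxiety. 5 × 0.251 = 1.3, 5 × 0.169 = 0.8 and 5 × 0.107 = 0.5 'small or larger' improvements at n = 12, 24 and 40. Table 2 lists 23 instruments measured pre and post (counting the pain inventory once). Over all of them the figures are 5.8, 3.9 and 2.5. Expected counts do not need independence between scales.

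**Sensitivity to the standardiser.** If d uses the baseline SD, the interval for d = 0.5 depends on the pre-post correlation, which the documents do not give. Assuming equal pre and post SDs and a correlation of 0.5, 0.7 or 0.8, it is -0.11 to 1.09, 0.01 to 0.98 or 0.08 to 0.90 at n=12, and 0.17 to 0.83, 0.23 to 0.76 or 0.27 to 0.72 at n=40.

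**The case against.** The strongest reply is that the labels do not stand alone. Section 9 tests first and describes effect sizes afterwards. A chance d of exactly 0.2 would sit beside p = 0.50, 0.34 or 0.21, not significant at an assumed 5% level at any of the three sizes. This stands against a reader who infers that labels are the plan's only reading of efficacy. It does not supply an interval, and the text leaves a non-significant result free to be called small or medium.

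A reader might also infer that a 'medium' label could mean anything from nothing to large throughout. The figures do not support that. The interval reaches zero only with 17 or fewer completers, and a chance 'medium' is rare from n=24 upward. At 40 completers the interval is still wide, from just under the small anchor to just over the large one.

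A third tempting inference is that several scales will be falsely labelled. The 23-instrument totals are an all-null scenario, not a forecast. They also include substance use, discrimination and a single sleep-duration item, which Table 2 files outside the function and pain domains.

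Finally, Section 9 does not exclude reporting native-unit change; a paired t-test is built on it. True, but reporting it is not stated either.

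**Conclusion.** The point holds as a reporting weakness in the secondary outcomes. The labelling rule carries no measure of precision and is not tied to the test. At the plan's own 12 to 40 completers, a 'small' improvement on d arises by chance 25% to 11% of the time when nothing has changed (36% to 26% on r). A 'medium' d of 0.5 is compatible with no change only at the low end of enrolment.

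These sizes rest on d being standardised by the SD of change, on the d anchors being used as thresholds, and on a 95% level. A baseline-SD standardiser with a pre-post correlation above 0.5 would narrow the intervals.

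It would be wrong to conclude that a study decision is at risk. The go/no-go benchmarks in Table 4 concern participation, session completion and fidelity, and none uses an effect-size label. This is a cheap improvement.

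**What to change.** In Section 9, replace the labelling rule with text to this effect: for each outcome, report the mean (or median) change in native units, such as metres, steps per day or scale points, with a 95% confidence interval, and the standardised effect with its 95% interval; the interval, not the point estimate, is interpreted. State which SD standardises d. If verbal labels are kept, give the label at both ends of the interval.

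The cost is a few sentences in the analysis section, made before the data are analysed. Standard or bootstrap intervals serve for every outcome, and no visit, measure or sample-size change is needed. The downside is less favourable wording of the preliminary efficacy results, particularly if enrolment ends near the low end.

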The 10-week *GetActive+* program will be conducted either in-person or via Zoom and led by a fully trained member of study staff. Spanish speaking groups will follow the same structure and will be led by a fully trained native Spanish speaking member of study staff. In the event that group sessions are conducted virtually, we will use an MGB Zoom account. Zoom specifically states that their software is equipped to keep information secure, and the software does not have access to identifiable information. Zoom is HIPPA compliant, MGB approved, and the current video software standard for patient care within our Department of Psychiatry. Participants will be encouraged to attend as many group sessions as possible and complete their home practice assignments between sessions. Participants who can't attend the group sessions will be offered make-up sessions. Throughout these ten weeks, the RA will send participants daily reminders via text message to practice program skills, log home practice, and attend the sessions (contingent on their consent to receive such text messages). These text messages will be sent using Twilio, which will be integrated with our REDCap database. Participants will have the option to attend a 5-10 minute 1-on-1 medical check-in with the nurse practitioner before or after each group session. Within 3 days after the last group session, participants will complete the in person post-program assessments and pick up their ActiGraph to wear for the next 7-10 days (see section 6). They will return the ActiGraph in person or via a pre-paid envelope.

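### The acceptability benchmark in Table 4 is printed without percent signs, and as printed a pilot of up to 50 people with 10 sessions each cannot meet it

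*Combined protocol and SAP*

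**What the plan says.** Section 9 refers to Table 4 for the a priori benchmarks, and the last column of that table is headed as holding the Go/No-Go criteria. The acceptability row, assigned to R61 Aim 2 and R33 Aim 3, reads ">=75 enrolled complete >=75 sessions", followed by qualitative feedback. Neither number carries a percent sign.

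The rows on either side do carry one. Feasibility is ">= 75% agree to participate in intervention" and fidelity is ">=75% of sessions components delivered by clinicians in the clinic as intended".

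The size of the pilot is given twice. The note to Figure 2 in Section 2 has "Total number of patient participants (up to N=50" and Section 3 plans "3-6 groups of approximately 5-10 participants each (up to N=50". Section 6 delivers the programme "over the course of 10 weekly sessions". The compensation paragraph of Section 6 pays a bonus to participants who attend 8 or more of the 10.

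On the standing of acceptability, Section 3 aims to "establish feasibility (primary), acceptability, and fidelity", which attaches the word primary to feasibility alone. Section 6 lists all three among the primary outcomes of the open pilot. The acceptability benchmark is not restated elsewhere in the document.

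**The concern.** A Go/No-Go benchmark should be a number that the study could reach or miss depending on what happens. As printed, this one lies outside the range of the pilot on both of its parts: more people than can enrol, and more sessions than any person is offered.

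Section 2 makes it an aim of the pilot to judge acceptability against its benchmark, and Section 6 counts acceptability as a primary outcome. With no second statement of the rule to fall back on, the threshold would have to be inferred. If that is done after attendance is known, the benchmark is no longer fixed in advance.

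**Working it through.** **Inputs**

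- Benchmark as printed: 75 enrolled, 75 sessions (Section 9, Table 4).
- Maximum enrolment: N = 50 (Sections 2 and 3).
- Sessions offered per person: 10 (Section 6).
- Number of groups: 3 to 6 (Section 3).
- Attendance bonus: at least 8 of 10 sessions (Section 6).

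No sample-size or power formula lies behind the benchmark, so there is no derived figure to reproduce first.

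**Step 1: both numbers read as counts**

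- Participants: 75 > 50, short by 75 − 50 = 25 even at full enrolment.
- Sessions per person: 75 > 10, that is 75 / 10 = 7.5 times the number offered.
- Sessions as scheduled group meetings over the whole pilot: 3 × 10 = 30 to 6 × 10 = 60, both below 75.
- Sessions as attended person-sessions: the maximum is 50 × 10 = 500, so 75 could be reached. The participant condition still fails, because 75 > 50.

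No reading as counts satisfies both parts.

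**Step 2: one percent sign restored**

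- Only on sessions: 75 participants are still required from at most 50.
- Only on participants: each would still need 75 sessions out of 10. Pooling the sessions would make this attainable but nearly empty. With 38 qualifying people, 75 / 38 ≈ 2 sessions each would be enough.

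Both signs are needed for a sensible rule.

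**Step 3: both percent signs restored**

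- Sessions: 0.75 × 10 = 7.5. Since 7/10 = 70% falls short and 8/10 = 80% passes, the threshold is 8 of 10. This matches the attendance bonus.
- Participants, 0.75 × N rounded up:

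| Enrolled | 0.75 × N | Needed |
|---|---|---|
| 20 | 15 | 15 |
| 30 | 22.5 | 23 |
| 40 | 30 | 30 |
| 50 | 37.5 | 38 |

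Each of these is attainable.

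**The case against.** The strongest reply is that this is a typographical slip with an obvious meaning. The neighbouring rows print the sign, the 8-of-10 bonus agrees with 75% of 10 rounded up, and no sample size, analysis or data collection depends on the literal reading. All of that stands as evidence of intent. It does not remove the point: the bonus is a payment term rather than a benchmark, and the slip is in the decision threshold itself.

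The signs may also have been lost when the PDF was read by a program. That cannot be excluded. It is less likely because the sign survives in two other rows of the same table, but it is the reason to check the original first.

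A reader might infer that the pilot is bound to be a No-Go on acceptability whatever the attendance. The documents do not support that. The same cell lists qualitative feedback, and nothing says how the number and the feedback combine, so a failed number is not shown to decide the row.

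A reader might also see a second defect in Section 3, where people who miss a group session "will be offered make-up sessions" without a statement that these count as completed. The ordinary reading is that a make-up replaces the missed session. Any estimate of its effect on the result would need attendance and uptake assumptions that the documents do not give, so it forms no part of this point.

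**Conclusion.** The benchmark is wrong as written for R61 Aim 2 and should be corrected. The printed figures are 75 participants against a maximum of 50 and 75 sessions against 10 per person. On the most generous count reading, the participant half alone still fails. This is an error in stating the threshold. It is not evidence that the design cannot succeed, because with both percent signs the rule is coherent and attainable.

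The unattainability rests only on the stated maximum enrolment and session count. The diagnosis of two omitted signs is an inference from the neighbouring rows and the attendance bonus, and it depends on the original PDF also lacking them. The participant half applies to R61 Aim 2 alone, because the document does not give the size of R33 Aim 3.

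**What to change.** 1. Check the acceptability cell against the original PDF.
2. If the signs are absent there, restate the row before analysis as: *at least 75% of all enrolled participants complete at least 75% of sessions*. Naming all enrolled participants as the denominator keeps those who leave early in the count.
3. Add a table note for R61 Aim 2 only: at least 8 of 10 sessions, completed by at least 38 participants if 50 enrol (30 of 40, 23 of 30, 15 of 20). These counts should not be carried into R33 Aim 3.

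The cost is a small wording change and one table note. No new data, analysis or budget is needed. If the original PDF already prints the signs, only the optional note remains.
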